## **6. DOSING DELAYS/DOSE MODIFICATIONS**

Patients will obtain their medications from their respective pharmacies. Women randomized to Arm 1, will be instructed to take one tablet of baby ASA 81mg per day while those in Arm 2, will be asked to simultaneously take 2 tablets per day for a total of 162mg.

Therapy will be prescribed at the baseline visit to be initiated before 16 weeks of gestation. Aspirin therapy will continue until a week prior to planned delivery or upon admission for unplanned/imminent delivery as per routine clinical care.

Aspirin is an over the counter medication and comes in very large pill containers thus rendering pill counts unpractical. Adherence will be assessed using a validated questionnaire.

Dose modifications are not planned. If for a clinical reason, the participant or their healthcare providers have a concern or issue with the randomized dose; then that participant can be taken off the study dose and, with their permission, would be observationally monitored in an intention to treat analysis.

## **7. ADVERSE EVENT REPORTING REQUIREMENTS**

AE monitoring will be conducted throughout the course of the study and will be assessed at each visit. AEs will be reported to the IRB as indicated by their regulations.

## **8. PHARMACEUTICAL INFORMATION**

Clinical trials evaluating the benefits of low-dose ASA have used a wide range of doses from 60mg to 150mg orally daily with low-dose being defined as less than 325mg per day. ASA is currently the only prophylactic therapy for PE in high-risk women to be recognized by the US Preventive Task Force (in accordance with the World Health Organization) and should be initiated early in the second trimester of pregnancy, before 16 weeks of gestation (4).

## **9. CORRELATIVE/SPECIAL STUDIES**

There are no planned correlative or special studies.

## **10. MEASUREMENT OF EFFECT**

The primary objective of this study is to evaluate the protective effect of ASA on the risk reduction of preterm PE and PE with severe features, and measure whether a dose-effect exists.

The secondary objectives of our study include to:

- Evaluate and compare the adherence of pregnant women to 81 mg and 162 mg of daily low-dose aspirin using a validated, Simplified Medication Adherence Questionnaire (SMAQ).
- Compare maternal and fetal outcomes in pregnant women at a high risk for preeclampsia who are treated with either 81 mg or 162 mg of daily aspirin during pregnancy, including preeclampsia  $\geq$  37 weeks, severe maternal hypertension, preterm delivery, fetal growth restriction, placental abruption and maternal/fetal mortality.
- Compare the time-to-event for developing PE across the 2 treatment groups.

## **11. DATA REPORTING / REGULATORY CONSIDERATIONS**

### **11.1 Data Collection**

Data collection will be done through a secure RedCap database. Data collected is described in section "5. Study Procedures". Data will only be exported without protected health identifiers for data analysis.

The name and identifiers (date of birth and medical record number) of patients who were screened for the study but were not eligible or did not consent to being in the study will be stored in a secure RedCap database until the end of the study and then, deleted. These identifiers will only be accessible to the study personnel in order to prevent re-screening and approaching again patients that are ineligible or unwilling to participate in our study. Laboratory personnel and other research personnel that is not involved in participant recruitment or follow up will not have access to identifiers.

Bio samples will be stored in a de-identified manner in the Nephrology research lab ([name] lab) in [name].

### **11.2 Regulatory Considerations**

IRB approval will be obtained prior to the initiation of the study. IRB approval renewals will be sought as per routine for the duration of the study. All protocol amendments will be made by the Principal Investigator.

## **12. STATISTICAL CONSIDERATIONS**

### **12.1 Study Design/Endpoints**

Subjects will be recruited from the New York Presbyterian – Weill Cornell and Queens campuses' affiliated Obstetric Clinics and The Hypertension Center. Patients will be screened for eligibility and if eligible and consented, will be randomized to one of 2 arms: ASA 81mg daily vs ASA 162mg daily, to be started before 16 weeks' gestation. Randomization will be electronically performed through the RedCap study portal. This will be an open label pilot study. Those patients who are randomized to the 162mg group, will be instructed to take two 81mg tablets simultaneously. Patients will be instructed to continue ASA until delivery.

Subjects will be seen (as per routine clinical care) monthly in the second trimester and at least every 2 weeks thereafter. They will then be evaluated for antepartum complications and PEC. Study participants will be assessed by study personnel in synchrony with their routine obstetric appointments at baseline (<16 weeks), 18-22 weeks, 24-28 weeks, 34-38 weeks, delivery and postpartum (1-6 weeks after delivery). The schedule of evaluations is described in section “5.1. Schedule of Evaluations”.

Blood pressure, medication reconciliation with questionnaire, and chart review will be performed at each visit. Records will be reviewed to document laboratory tests and fetal testing. If the patient is diagnosed with PE at a time point other than the pre-set time points, we would collect the information as part of a “study outcome” visit. Delivery records will also be collected to include: blood pressure, medication regimen, laboratory tests, physical exam, imaging, placental pathology reports, operative records, birth and neonatal outcomes. Diagnosis of PE will be made by clinical chart review and ascertained by 2 independent adjudicators (co-investigators) (as detailed in section “5.3. Outcome Allocation”). If there is a disagreement, a 3rd adjudicator will be asked to review the chart.

The study will be done in 2 stages. The first stage will aim to recruit 50-100 patients within the first 6 months to a year in order to evaluate feasibility, safety and determine the incidence of preterm PE and PE with severe features in order to calculate/verify the adequate sample size needed for this study’s completion. The stages are further detailed in section “12.3 Sample Size/Accrual Rate”.

## **12.2 Treatment Regimens**

Arm 1: 81mg oral ASA daily.

Arm 2: 162mg oral ASA daily.

Patients will obtain their prescriptions from their respective pharmacies. Women in Arm 1, will be instructed to take one tablet of 81mg aspirin per day; those in Arm 2, will be asked to take two tablets simultaneously orally once per day. Therapy will be initiated at the baseline visit and continue until 1 week before planned delivery or upon admission for unplanned/imminent delivery as per clinical routine.

## **12.3 Sample Size/Accrual Rate**

A sample size of 394 participants (197 for each group) will allow us to detect at 7.1% difference in the incidence of PE between the 2 groups. This is based on prior data reporting an incidence of PE of 8.6% and 1.5% for 81mg and 150mg of ASA respectively (10, 12) with a target 85% power and a Type 1 error rate (alpha) of 5% (two-tailed). Assuming a response rate of 50%, we will aim to screen 788 women.

The above calculation is however only theoretical and very approximate. The incidence of PE in women on 162mg of ASA is not known and the incidence of PE in the 81mg of daily ASA that has been reported in the above-mentioned literature (10) appears to be far below the incidence of PE of 33.6% in

our patient population (16). Our elevated rate of PE likely stems from referral bias and from the fact that, at the time of this study, aspirin was still not widely prescribed as it was not standard of care yet.

The study will therefore be done in two stages:

Stage 1: Pilot stage to assess feasibility and ensure feasibility and safety with the randomization of 50-100 patients. The incidence of PE in the 2 groups will be evaluated and serve to calculate a sample size with a power of 85% to detect the observed difference between the two groups (adjusting for the interim analysis effect).

We will recruit 50-100 patients in the initial stage of this trial. We have obtained an approximate estimation for the number of patients we see in the Women's Health Practice and in J130 that would meet eligibility criteria for our study at <16 weeks gestation with USPTF high risk factors for the development of pre-eclampsia. We have sampled 3 separate months of the year so as to account for holidays, change in faculty coverage, and seasonality. In the month of January, there were 9 eligible patients; in October, there were 32 eligible patients; and in June, there were 29 eligible patients. Given the variability from month to month, and assuming a 50% response rate, 11 patients a month could potentially be randomized. Assuming a 75% adherence rate, we anticipate having approximately 50 patients for initial assessment of feasibility and safety by the end of 6-12 months, after which we would perform a more accurate power analysis and continue with the second stage of our study.

Stage 2: Larger, powered, clinical trial. Proceed with randomization of the remaining patients to the accrual ceiling as determined by Stage 1. The interim analysis that was used to establish an accurate sample size calculation will be taken into account.

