### Protocol Summary

Full Title:	A Randomized Controlled Trial Comparing Low Doses Of Aspirin In The Prevention Of Preeclampsia (ASAPP)
Short Title:	ASAPP
Clinical Phase:	III
Principal Investigator:	[name]
Sample Size:	N= 400 which may be modified after the first stage of our study
Accrual Ceiling:	400
Study Population:	Pregnant women < 16 weeks of gestation at high risk of PE (preeclampsia in a prior pregnancy, multifetal gestation, chronic hypertension, Type 1 or 2 diabetes, renal disease, autoimmune disease).
Accrual Period:	5 years
Study Design:	Open-label, randomized clinical trial. First stage: pilot to determine feasibility and sample size and second stage: completing the clinical trial
Study Duration:	9 months for each patient (from recruitment until 6 weeks postpartum)
Intervention Description:	Randomized to 81mg vs. 162mg of aspirin per day
Primary Objectives:	To compare the incidence of preterm PE and PE with severe features in women treated with 81mg to those treated with 162mg of aspirin per day.
Secondary Objectives:	

Evaluate and compare the adherence of pregnant women to 81 mg and 162 mg of daily low-dose aspirin using a validated, Simplified Medication Adherence Questionnaire (SMAQ).

Compare maternal and fetal outcomes in pregnant women at a high risk for preeclampsia who are treated with either 81 mg or 162 mg of daily aspirin during pregnancy, including preeclampsia <math>\geq</math> 37 weeks, severe maternal hypertension, preterm delivery, fetal growth restriction, placental abruption and maternal/fetal mortality.

To compare the time-to-event for developing PE for women treated with 81mg vs. 162mg of aspirin per day.

To assess the adherence to low dose aspirin in pregnant women that are a high risk for preeclampsia and compare adherence rates for women on 81mg vs 162mg of aspirin per day.

Exploratory Objectives:	To assess the impact of specific co-morbidities (diabetes, chronic hypertension, renal disease and autoimmune disease), blood pressure

*control, age and race on the relationship between treatment group and PE incidence.*

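### Section 12.3 re-sizes the trial on the difference observed in 25 to 50 women per arm, so the final N is largely chance; the target and the maximum N should be fixed in advance.

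*Combined protocol and SAP*

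**What the plan says.** Section 12.3 starts from 394 women (197 per arm), which "will allow us to detect at 7.1% difference in the incidence of PE between the 2 groups". The inputs are literature rates of 8.6% and 1.5%, 85% power and two-sided 5% alpha. The section then calls this calculation rough and cites a PE incidence of 33.6% in the site's own population, with the caution that "Our elevated rate of PE likely stems from referral bias".

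It therefore adds a Stage 1 of 50-100 randomized women, expecting about 50 to be available for the first assessment. PE incidence is examined in the two groups and used to "calculate a sample size with a power of 85% to detect the observed difference between the two groups (adjusting for the interim analysis effect". For Stage 2 the text reads "Proceed with randomization of the remaining patients to the accrual ceiling as determined by Stage 1", followed by "The interim analysis that was used to establish an accurate sample size calculation will be taken into account".

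Three other places bear on this:
- The Protocol Summary gives the sample size as "N= 400 which may be modified after the first stage of our study". A separate row sets the accrual ceiling at 400 without qualification.
- Section 12.1 asks Stage 1 to "evaluate feasibility, safety and determine the incidence of preterm PE and PE with severe features in order to calculate/verify the adequate sample size".
- Section 2.2 says that after a null result the team would consider whether a larger trial is reasonable.

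**The concern.** A sample size should be set for a difference worth detecting. Here it is set for whatever difference appears in 25 to 50 women per arm. A chance large difference gives a trial that is too small, a chance small one gives a very large trial, and a tie gives no number at all. The plan has no rule for a tie or a reversed difference. The 7.1 points used at the outset are not carried into the recalculation, and Stage 2 takes its ceiling from Stage 1. At stake is whether the N that is finally chosen, and the 85% attached to it, mean anything. The promised interim adjustment has no named method, and an alpha adjustment would in any case not steady N.

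**Working it through.** **Inputs (Section 12.3).** p1 = 0.086, p2 = 0.015, d = 0.071; two-sided 5% (z = 1.960); 85% power (z = 1.036); Stage 1 of 25 or 50 per arm (50-100 women at 1:1).

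**Reproducing 394.** With p̄ = (p1 + p2)/2 = 0.0505:

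n0 = [1.960·√(2p̄(1−p̄)) + 1.036·√(p1(1−p1) + p2(1−p2))]² / d² = (0.607 + 0.317)² / 0.00504 = 169.2.

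Continuity correction: n = (n0/4)·[1 + √(1 + 4/(n0·d))]² = 42.3 × 2.1545² = 196.4, rounded up to 197 per arm, or 394. This matches the plan. Without the correction the result is 170 per arm (340).

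**How little Stage 1 can say.** Expected events are 25 × 0.086 = 2.2 vs 25 × 0.015 = 0.4, or 4.3 vs 0.8 at 50 per arm. The 95% half-width of the difference, 1.96·√[(0.0786 + 0.0148)/m], is 12.0 points at m = 25 and 8.5 at m = 50, around an effect of 7.1 points.

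**What one event does.** The same formula applied to observed counts gives these totals:
- 25 per arm: 3 vs 0 gives 170; 3 vs 1 gives 460; 2 vs 1 gives 1,362.
- 50 per arm: 5 vs 1 gives 362; 4 vs 2 gives 1,362; 4 vs 3 gives 6,042.

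**Distribution of N under the rule.** Exact enumeration of both binomials at 8.6% vs 1.5%, no cap:

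| Stage 1 result | 25 per arm | 50 per arm |
|---|---|---|
| Tie, no finite N | 15% | 5% |
| Reversed difference | 5% | 2% |
| N < 200 | 27% | 14% |
| N 200-400 | 23% | 41% |
| N > 400 or none | 51% | 44% |

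The last three rows cover all pilots; ties are included in the last row.

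**Power of the whole procedure.** This was simulated with an unadjusted chi-square, Stage 1 women kept in the analysis, a cap of 400 and ties sent to the cap. Results are for 25 / 50 per arm:
- 8.6% vs 1.5%: 86% / 91%. With an inverse-normal combination test it is 81% / 86%.
- 33.6% vs 26.5% (assumed: same 7.1 points at the site rate): 32% / 34%. A plain trial of 400 also has 34%, so the ceiling is the limit there.
- 33.6% vs 5.9% (assumed: planning risk ratio, 0.336 × 0.015/0.086): 99% or more.

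**Type I error.** If Stage 1 data are pooled with no adjustment, it is about 5.5-7.4% over null rates of 5% to 33.6% and caps of 400 to 4,000.

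**Why the effect scale matters.** By the plan's formula, 7.1 points from 33.6% needs 1,552 women; the planning risk ratio at 33.6% needs 86.

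**What 400 can detect at 85% power.** About 7.1 points from 8.6%, 11.0 from 20% and 13.7 from 33.6%.

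**The case against.** The best defence is that average power at the planning rates is adequate and that the plan promises to account for the interim look. Both statements are right. A reader might infer from the unstable N that the trial is underpowered, or that its type I error is inflated. The documents support neither. Power at 8.6% vs 1.5% with a 400 cap is near or above 85%. The inflation arises only if the promised adjustment is not made; what is missing is its method.

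A reader might also infer that the plan has no ceiling. The Protocol Summary does state 400, and only its sample-size row is marked as modifiable. The fault is that Section 12.3 lets Stage 1 determine the ceiling, so the two places conflict.

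Section 2.2 does offer a response to a null result. It is discretionary, and it does not say what N follows from a tied or reversed Stage 1.

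It is tempting to claim that fixing 7.1 points and re-estimating the pooled rate would nearly always give the right N. That holds only if 7.1 points is the truth. At an assumed 8.6% vs 4.3% the requirement is 1,262. With a cap of 4,000, a 7.1-point target would average about 490 women and 48% power, against 67% / 80% for the unadjusted rule with a larger average N. A fixed target gives power for a stated difference; it does not find the true one.

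**Conclusion.** The rule is wrong as written and should be fixed. At the plan's own rates, half of pilots at 25 per arm and 44% at 50 per arm lead to N above 400 or to none, and 27% / 14% lead to N below 200. The 85% is therefore not a property of the rule, and no alpha adjustment repairs that.

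The enumeration needs only the plan's rates, its formula and 1:1 allocation. The power and type I figures also assume that Stage 1 women stay in the final analysis (inferred from the Stage 2 wording) and that ties go to the cap. Every rate pair other than 8.6% vs 1.5% is an assumption. The 33.6% is all PE in an earlier cohort, which the plan attributes to referral bias and limited aspirin use, so it is only an upper illustration. Depending on which pair is assumed, power at 400 runs from about a third to almost 100%; that reflects the ceiling and the true effect more than the rule.

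**What to change.** Replace the re-sizing sentence in Section 12.3 with:

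> Before Stage 1 outcomes are seen by arm, the sponsor will fix a justified, clinically relevant target for the primary outcome (preterm PE or PE with severe features), stating whether it is an absolute difference or a relative reduction, and a maximum N. Stage 1 will estimate the incidence of that outcome in both arms combined. N will be recalculated once for 85% power (two-sided 5%) at the fixed target. It may be raised up to the maximum but not reduced below 394. If the recalculated N exceeds the maximum, the power or detectable difference at the maximum will be restated. No by-arm efficacy tabulation will be used for sample size; by-arm safety review is unaffected.

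State the same maximum in the Protocol Summary and in the Stage 2 paragraph. A pooled rate meets the purpose that Section 12.1 gives to Stage 1.

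Do not carry 7.1 points over by default. It is a literature difference in PE, and the primary outcome is narrower.

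If the maximum stays at 400, a floor of 394 leaves six women of room. In that case drop the re-estimation, recruit 400 (about 93.5% power at the planning rates by uncorrected chi-square) and state what 400 can detect.

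The documents do not say whether by-arm results have been seen. If they have, take the target from outside the Stage 1 data and name a method that protects alpha, such as a combination test with pre-set weights.

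Cost: the sponsor must commit to a target and a maximum early and give up the by-arm efficacy look for sizing. N will not adapt if the true effect differs from the target. The pooled rate is also imprecise: at 5.05%, 1.96·√(0.0505 × 0.9495/n) is 6.1 points with 50 women and 4.3 with 100, so about 100 in Stage 1 is preferable.

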#### **12.4 Stratification Factors**

A secondary objective of this study is to assess the impact of specific co-morbidities (diabetes, chronic hypertension, renal disease and autoimmune disease), blood pressure control, age and race on the relationship between treatment group and PE incidence.

#### **12.5 Analysis of Secondary Endpoints**

Standard descriptive statistics (such as mean or median, range and percentage) will be computed for patient characteristics. Baseline characteristics will be compared across treatment arms using Mann-Whitney U (for non-parametric variables), student's t-test (for normally distributed variables) or Chi-square tests (for categorical variables). Group differences in the incidence of preterm PE (<37 weeks) and PE with severe features (our primary outcome) will be tested using Chi-square.

As secondary analyses, multivariate logistic regression will be used to further assess the impact of co-morbidities (diabetes, chronic hypertension, renal disease and autoimmune disease), blood pressure, age and race on the relationship between treatment group and PE incidence. An exploratory analysis will be made to compare the time-to-event for PE across the 2 treatment groups using a log-rank test and a cox-regression model to adjust for the above-mentioned possible confounders. We will use Stata 15 (StataCorp. College Station, TX) for data analysis.

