## **2.2 Rationale**

PE is a morbid and potentially lethal complication of pregnancy and is more common in women with specific risk factors. ASA is currently the only prophylactic therapy for PE in high-risk women to be recognized by the US Preventive Task Force and should be initiated early in the second trimester of pregnancy, before 16 weeks of gestation (4). However, currently there is no literature comparing various low-dose aspirin formulations in the risk reduction of PE. In the United States, the currently available low-dose aspirin is over the counter and is found in 81mg tablets. Therefore, when clinicians initiate therapy with low dose ASA, they may prescribe 1 or 2 tablets of 81mg ASA per day depending on personal preference cannot be assisted by evidence to guide their decision.

The proposed study would determine the incidence of preterm PE or preeclampsia with severe features in women taking either 81mg or 162mg in a randomized setting, from two centers (Weill Cornell/New York Presbyterian and New York Presbyterian Queens). We hypothesize that the information gained from this trial will permit a more accurate sample size calculation for a larger clinical trial powered to accept or reject our testing hypothesis.

If our hypothesis is rejected and 162mg of daily ASA is not associated with a lower incidence of severe or preterm PE in pregnancy compared to 81mg, this may be due to lack of power to detect a smaller effect. We would then evaluate the feasibility and results and determine whether a larger trial is reasonable.

cfRNAs may provide further insight into the pathophysiology of the protective effect of ASA on the development of PE in high risk women. Assessing molecular pathways in the development of PE may allow opportunity for earlier diagnosis, specific triaging of patients to closer monitoring and further development of preventative or curative treatment strategies.

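### The primary outcome gets only an unadjusted chi-square test, with no effect estimate or confidence interval, although the plan intends to interpret a null result

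*Combined protocol and SAP*

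**What the plan says.** All places are in the combined protocol and SAP.

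- **Primary analysis (12.5).** Preterm PE "and PE with severe features (our primary outcome) will be tested using Chi-square". No effect measure or interval is named for this outcome here or elsewhere.
- **Adjusted models (12.5).** "As secondary analyses, multivariate logistic regression will be used to further assess the impact of co-morbidities", blood pressure, "age and race on the relationship between treatment group and PE incidence". The co-morbidities are diabetes, chronic hypertension, renal disease and autoimmune disease. An exploratory time-to-PE analysis follows, "using a log-rank test and a cox-regression model to adjust for the above-mentioned possible confounders". Site is in neither model. Nor are prior PE and multifetal gestation, which are two of the six qualifying risk factors in 3.2.
- **Sites and randomisation.** Section 2.2 describes women "from two centers (Weill Cornell/New York Presbyterian and New York Presbyterian Queens"). Section 12.1 says "Randomization will be electronically performed through the RedCap study portal" and mentions no strata. Section 12.4 is headed Stratification Factors but names none. It opens "A secondary objective of this study is to assess the impact of specific co-morbidities", which is an objective about effect modification.
- **Use of the result (2.2).** "If our hypothesis is rejected and 162mg of daily ASA is not associated with a lower incidence" of severe or preterm PE, the plan says low power to see a smaller effect may be the reason. The team would then decide whether a larger trial makes sense.

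**The concern.** Section 2.2 sets the trial a question that the analysis in 12.5 does not answer. Whether a null result leaves room for a worthwhile effect depends on which effects the data still allow, and a confidence interval shows that. A p-value above 0.05 does not separate a trial that has ruled out its target difference from one that has learned little.

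The second issue is efficiency. Women qualify through any of six risk factors at two centres. If those factors predict PE, adjusting for them sharpens the comparison at no cost in patients. The factors are recorded at entry, but neither the randomisation as described nor the primary analysis uses them. The adjusted models that do exist are not stated to be for the primary outcome.

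**Working it through.** **1. The plan's own figure.** Inputs from 12.3: 8.6% versus 1.5%, two-sided alpha 5%, power 85%, so δ = 0.071 and the mean rate is 0.0505.

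- Uncorrected: n = [1.960·√(2·0.0505·0.9495) + 1.036·√(0.086·0.914 + 0.015·0.985)]² / 0.071² = 169.2, so 170 per arm.
- Continuity-corrected: (169.2/4)·[1 + √(1 + 4/(169.2·0.071))]² = 196.4, so 197 per arm and 394 in total.

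This matches the stated 394, so the trial was sized on a crude comparison of two proportions. By exact enumeration, the Pearson chi-square at 197 per arm has 93.2% power at these rates.

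**2. What an interval would show after a null result.** Assume 5% events in each arm, close to the planned mean of 5.05%.

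- Risk difference: 1.96·√(2·0.05·0.95/197) = 0.043, so ±4.3 points.
- Risk ratio: SE of the log = √(2·0.95/(197·0.05)) = 0.439, and exp(±1.96·0.439) gives 0.42 to 2.4.

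Such a result would exclude the 7.1-point target but would still allow the risk to be more than halved or doubled. Section 2.2 needs both facts, and the chi-square reports neither.

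**3. What adjustment would add.** The documents give no PE rates by risk factor or by site, so every prognostic strength below is an assumption. All figures are simulated power at 197 per arm, with Monte Carlo error of up to about 0.8 point per figure.

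| Setting | Crude chi-square | Adjusted |
|---|---|---|
| 8.6% v 1.5%, two strata, two-fold risk gap | 93.2% | 93.2% (Mantel-Haenszel) |
| 8.6% v 1.5%, two strata, four-fold gap | 92.9% | 93.3% (Mantel-Haenszel) |
| 8.6% v 1.5%, risk score with AUC 0.83 | 93.7% | 96.4% (logistic) |
| Strata at 33.6% and 8.6%, 50/50 mix, RR 0.55 | 73.3% | 75.8% (Mantel-Haenszel) |
| Same strata, 30/70 mix, RR 0.55 | 58.8% | 62.1% (Mantel-Haenszel) |
| Mean 21.1%, two-fold gap, RR 0.55 | 73.0% | 73.6% (Mantel-Haenszel) |
| 33.6% v 20.2%, three factors of OR 3 | 85.8% | 90.1% (logistic) |
| 33.6% v 20.2%, risk score with AUC 0.82 | 87.4% | 94.0% (logistic) |
| 20% v 10%, risk score with AUC 0.82 | 80.8% | 89.8% (logistic) |

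Adjusting for site alone (OR 1.5 to 2) gains at most about 0.7 point. At the planned rates an unadjusted likelihood-ratio test gains as much, so that part comes from the change of test and not from the adjustment.

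**4. Validity of the crude test.** With no true effect at 33.6%, the chi-square rejected in 4.4% to 5.4% of simulated trials.

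**5. How many covariates the data can carry.** Expected events at the planned rates are 197·0.086 + 197·0.015 = 19.9, of which about 3 are in the 162 mg arm. Site plus all six risk factors would be seven terms, or about 3 events per term (19.9/7). Cross-classified, they make 2⁷ = 128 cells for 394 women. Three binary factors make 8 strata of about 49 women and 2.5 events each, if evenly spread. The chance of no event at all in the 162 mg arm is 0.985¹⁹⁷ ≈ 5%, so an estimator that fails with zero events needs a fallback.

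**The case against.** The strongest reply is that a crude primary test with adjusted secondary models is a legitimate design. That stands. No stratified randomisation is described, so leaving out site does not invalidate the chi-square. Chance imbalance between the arms is already covered by its error rate and is not bias.

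The reply also says that adjustment is partly present. The secondary logistic model would give an odds ratio and the Cox model a hazard ratio. Section 12.3 uses incidence of PE loosely for the endpoint behind the sample size, so the same words in 12.5 may be meant to cover the primary outcome. That is possible, but the text does not say so. On either reading, no absolute or relative risk with an interval is specified for the primary outcome.

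A reader might go further and infer that baseline risk is known to vary about four-fold within this trial (33.6% against 8.6%), so that the plan discards substantial power. The documents do not support this. Section 12.3 gives these as a literature rate on aspirin and a rate in the sites' own population. It attributes the high local rate to referral bias and to limited aspirin prescribing at that time. They are not strata of this trial, and both are given for PE overall. The RR of 0.55 used in some rows above is also an assumption. The plan's own rates imply 1.5/8.6, about 0.17.

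**Conclusion.** The point holds as one of reporting and efficiency, not of validity. The firm part needs no assumption about risk factors: 12.5 specifies no estimate or interval for the primary outcome, while 2.2 depends on one. At 5% events per arm, the missing interval would be about ±4.3 points.

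The efficiency part is real in direction but uncertain in size. The gain is under about 0.5 point for a two-stratum adjustment at the planned rates, and up to about 3 points there with strongly prognostic covariates. It is about 3 points under an assumed four-fold risk gap with RR 0.55. It reaches about 7 points near 33.6%, or 9 points at 20% versus 10%, only with a risk score stronger than a short covariate list may achieve. For site alone it is at most about 0.7 point. The documents do not show that a large amount of power is being lost.

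**What to change.** In 12.5:

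- Make the primary analysis a risk difference and a risk ratio, each with a 95% CI, for the primary outcome. Adjust by Mantel-Haenszel, or by logistic regression with marginal standardisation.
- Adjust for a short fixed list of factors recorded before randomisation, for example site, chronic hypertension and prior PE. Choose the list without reference to outcomes by arm, including those from Stage 1.
- Name a fallback for sparse strata, non-convergence or an arm with no events.
- Keep the crude chi-square as a supportive analysis.
- State which outcome the secondary logistic model uses.

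In 2.2, have a null result interpreted by the confidence interval: whether it excludes the target difference, and which effects it leaves open.

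The cost is a paragraph of SAP wording and a few lines of Stata, with no new data. The downside is sparsity. With about 20 events expected at the planned rates, adding all the entry risk factors would do more harm than good.
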